5.0 CLINICAL MANAGEMENT ISSUES

5.1 Adverse Events

The medical response to adverse events (AE) or serious adverse events (SAE) will be managed and assessed under the on-site direction of our medical team. An AE is defined as any unfavorable and unintended sign (including an abnormal laboratory finding), symptom, or disease temporally associated with the use of a medical treatment or procedure regardless of whether it is considered related to the medical treatment or procedure. An SAE is defined as the following: an AE that results in death, is life-threatening (even if temporary in nature), results in a permanent impairment of body function or permanent damage to body structure, hospitalization, prolongation of hospitalization, or medical or surgical intervention to preclude permanent impairment of a body function or permanent damage to a body structure, or represents a serious medical event.

AE associated with acute cannabis exposure may include the following: 1) likely effects: difficulty with balance, eye irritation, throat irritation, increased heart rate, possible low blood pressure, reversible problems with appetite; 2) less likely effects: changes in mood (euphoria or dysphoria), loss of memory, decreased ability to concentrate or think properly; 3) rare but

serious effects: dizziness, head and chest pressure, disorientation, agitation, combativeness, incoherence, or visual hallucinations.

If requested by the research team, a personal assessment of the participant will be performed. Participants will be followed by the research team until such time as the adverse event resolves. A Registered Nurse and/or research associate will consult with study PIs to discuss each adverse event. In the event of any uncertainty, the decision as to whether or not the adverse event is to be labeled a SAE will be made by a Medical Officer. If deemed not to be a SAE, the AE will be reported at the time of the UCSD IRB continuing review or annual review by the FDA and NIDA.

All AEs will be collected on an Adverse Event log which will include the Patient ID, date, visit number, time in 24-hour format, description of adverse event, date of resolution if applicable, determination if related to the study, and date reported to UCSD IRB and study sponsor (NIDA). All AEs experienced by the participant, i.e., from the time of study drug administration through the end of the study, will be reported on this log. Any AE or SAE so recorded will be reported annually to the Human Research Protection Program (HRPP) at UCSD. In the event of an SAE, the PIs will report SAE to the UCSD IRB within 10 days as required by the HRPP. Such data will also be promptly reported to NIDA. Any AE and SAE reported may result in revisions to the study protocol. If so, these revisions will be submitted to the UCSD IRB for review. Any unexpected fatal or life threatening experiences associated with the use of the drug (21 CFR 312[.32[c] [ii] [2]) will be reported to the FDA via telephone or facsimile transmission within 7 calendar days after NIDA's initial receipt of the information. In accordance with FDA Code of Federal Regulations, the investigators will be responsible for reporting of SAE's directly to the FDA using the mandatory reporting form FDA 3500A.

5.2 Toxicity

Our group has previously administered a similar dose of THC (3.5%) to participants in prior studies using both cigarettes (Wilsey B, Marcotte T, Tsodikov A, et al. A randomized, placebo-controlled, crossover trial of cannabis cigarettes in neuropathic pain. *J Pain*. Jun 2008;9(6):506-521) and vaporized cannabis (Wilsey B, Marcotte T, Deutsch R, Gouaux B, Sakai S, Donaghe H. Low-dose vaporized cannabis significantly improves neuropathic pain. *J Pain*. Feb 2013;14(2):136-148). In both studies his findings indicated that none of the participants receiving 3.5% THC exhibited any AE or SAE due to drug exposure. Based on the data he has collected, we do not anticipate AE or SAE due to acute THC exposure in the current study (1.4% to 1.9%). In addition, we will be recruiting participants with a history of cannabis use rather than cannabis-naïve individuals; therefore, there is also lower risk of a novel AE or SAE occurring in these participants.

CBD does not bind to the known cannabinoid receptors and its mechanism of action is yet unknown⁸⁶. The administration of CBD appears to be much less problematic compared to THC. In a recent study comparing oral THC, CBD, and placebo in healthy volunteers⁸⁷, CBD was well tolerated and there were no differences between oral CBD and placebo on symptomatic or physiological variables. Other work suggests that CBD may in fact attenuate some of the psychoactive effects of THC⁸⁸⁻⁹⁰. After an extensive literature review, Bergamaschi and

colleagues concluded that CBD is a substance with low toxicity⁹¹. Based on these findings, we do not anticipate that there will be AE or SAE due to acute CBD administration in the study. However, no specific research on vaporized combinations of THC/CBD has been performed and we will collect data at every visit on any adverse effects that occur.

5.3 Monitoring Participant Safety

Ongoing medical treatment for HIV will not be altered or modified in any way for research purposes. During the initial enrollment and screening process, participants will be informed about potential events that may occur as a result of cannabis exposure and will be asked to contact the staff if any adverse events occur during study participation. Vital signs will be monitored during the cannabis administration procedure at hourly intervals to monitor the participant's health status. At any sign of an adverse reaction (e.g. a change in blood pressure or heart rate or development of psychological distress), medical staff will be contacted. Participants will be monitored by medical staff until such time as the adverse event resolves. In the event of a medical emergency, participants can be transported to the UCSD Medical Center Emergency Room. Participants will remain in the laboratory under direct observation by nursing staff for 3.5 hours after the cannabis vaporization inhalations are completed. At that time a final vital sign and self-report status check will be made and upon satisfactory readings, the subject will be released and driven back to his/her domicile by taxicab or prearranged transportation. The return transport procedure also will be observed directly by staff to ensure compliance. In an emergency situation that occurs outside of the university where participants are in need of immediate help as a result of an adverse event, the participants will be informed that they should first call 911 and then report the incident to the study staff as soon as possible. During IMPACT participants will also receive regular text messages that will solicit information about any adverse events associated with their self-administered cannabis use. Participant text logs will be monitored on a daily basis to ensure that no serious problems have occurred and to supervise each individual's continuing participation in the study. Participants are informed that they may withdraw from the research at any time if they find any aspect objectionable.

6.0 CRITERIA FOR DISCONTINUATION

6.1 Criteria for Discontinuation of Cannabis Administration

All participants will be informed of the risks of the study and the anticipated and potential effects of exposure to vaporized cannabis. We will monitor participant status throughout the day of the cannabis administration sessions, including assessing blood pressure at regular intervals (60, 120, 180 minutes after drug administration).

Stopping rules for study subject discontinuation include:

- Pulse: pulse rate > 130 beats per minute or < 50 beats per minute
- Blood Pressure: systolic blood pressure > 160 mmHg or < 80 mmHg,
diastolic blood pressure > 100 mmHg or < 40 mmHg
- Respiratory: shortness of breath, respiratory rate > 22 breaths per minute, or oxygen saturation less than 92%
- Cardiac: chest pain

Neuro: confusion, loss of coordination, falling down, fainting
 Psych: panic attack, psychotic reaction (hallucinations, psychotic depression)

6.2 Premature Study Discontinuation

- 8.2.1 Pregnancy or breast feeding.
- 8.2.2 Request by the subject to withdraw.
- 8.2.3 At the discretion of the investigators, UCSD IRB, NIDA, or other agencies providing oversight, i.e., Research Advisory Panel of California.
- 8.2.4. Rare but serious side effects of cannabis administration as listed in Section 6.1.

7.0 STATISTICAL ANALYSIS PLAN

7.1 Aim 1 Measures and Analyses

Data will be assessed for normality and transformations applied as needed (e.g., log). Neuropathic pain before and after acute cannabis administration will be assessed by NPRS and the von Frey test. Plasma AEA and 2-AG will be measured with LC/MS. Flow cytometry will quantify the percentage of PBMC that express CB2, FAAH, and MAGL, including monocytes, CD4+ T-cells, and CD8+ T-cells. To examine the effect of different CBD/THC products on NP and EC biomarkers, we will use a linear mixed model with subjects treated as a random effect to model the response measures. This methodology takes into account the repeated measures aspect of the within-subjects crossover study design, incorporating information from observations for each subject at different treatment doses and multiple time points within each dose. For initial modeling, terms will include dose (0.01%, 5.1% - 4 puffs, and 5.1% - 8 puffs) CBD treated as a categorical variable), time (0, 60, 120 and 180 minutes after exposure treated as a continuous variable), and dose x time interaction. Additional terms will also be included for the sequence in which the treatments were administered (e.g., low CBD vs. medium CBD) and for second-order time (time²). The quadratic term is intended to model a U-shaped response curve if responses initially increase (or decrease), reach a maximum (or minimum), then decrease (or increase) back to baseline levels. For each outcome measure, each of these last 2 terms will be omitted from subsequent models and not reported if nonsignificant. Any potential factors that associate with outcome variables at the $\alpha = 0.20$ level in single-predictor analyses (history of light vs. heavy cannabis use, mode of prior cannabis use – i.e., engaging in smoking, or vaporizing, or both), time since last cannabis use before baseline, duration of cannabis use over lifetime, presence of adolescent cannabis use, duration of HIV infection, nadir CD4, viral load, gender, the presence of other non-cannabis analgesic medications, history of non-cannabis substance use disorders) will be included in the linear model. Dose effects at each time point will be assessed with mixed modeling after re-coding time as a categorical factor and including dose and dose x time terms (plus a term for sequence if this is significant in the initial model). Differences among doses will be evaluated using the Tukey honestly significant difference (HSD) comparison tests for differences of effects over all time points and contrasts within each

time point. All response observations, including information from subjects who do not complete all experimental sessions, will be included in the analyses. Similar mixed-model analyses will be performed on the primary pain outcome after adjustment for psychomimetic side effects (measured with the ARCI scale) to assess for effects of the study drug on pain independent of subjective responses. The proportion of subjects with a 30% pain reduction, a standard for effective pain reduction⁶⁰ will be compared between each of the doses with chi-square tests; we will also calculate the number needed to treat (NNT) for a 30% pain reduction rate. We will also conduct analyses to examine the association between pain and EC biomarkers, including AEA, 2-AG, FAAH, and MAGL expression. A 5% significance level will be used for all testing. The association of pain levels with HRV will use a linear mixed-effects model, adjusting for potential confounders as above. Within-subject correlation will be accounted for using subject-specific random intercepts and slopes.

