
SCHEMA

Effect of Cannabis Administration and Endocannabinoids on HIV Neuropathic Pain

DESIGN: Our objective is to assess PLWH who have neuropathic pain and are currently using cannabis, including light use (1-4 times per month) and heavy use (5+ times per month). These participants will be enrolled in a study that consists of two stages: Stage 1) PLWH will participate in a 6-month mHealth text messaging program (Individual Monitoring of Pain and Cannabis Taken, or IMPACT) that will examine the association between cannabis obtained from local dispensaries and changes in daily pain. Participants will return for a visit after 6 months for follow-up testing so we can examine longitudinal changes in neuropathic pain, neuropsychological performance and EC function. Stage 2) A double blind crossover study where we administer three different doses of vaporized cannabis to each participant that contain THC and varying concentrations of CBD (low, medium, high), including: a) 2 vials of 0.01% CBD + 1.9% THC, b) 1 vial of 0.01% CBD + 1.9% THC and 1 vial of 5.1% CBD + 1.4% THC, and c) 2 vials of 5.1% CBD + 1.4% THC. Here we will examine the acute effects of cannabis obtained from NIDA on pain intensity, blood endocannabinoid (EC) levels, and the relationship of pain with heart rate variability (HRV).

POPULATION: PLWH with neuropathic pain and current cannabis use.

STRATIFICATION: none

REGIMEN OR INTERVENTION

Three doses of cannabis (with varying concentrations of CBD) administered once per day on three separate days.

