7.4 Power Analyses

A recent study indicated a medium effect size (Cohen's $d = 0.46$) for CBD treatment that increased plasma AEA levels compared to an antipsychotic drug control condition²⁶. Preclinical models of neuropathic pain in mice demonstrate that FAAH inhibitors decrease hyperalgesia

and allodynia with large effect sizes (Cohen's $d = 4-5$)¹⁸. Our pilot HRV data indicate a medium to large effect size (Cohen's $d = 0.8$) for reduced RMSSD in PLWH with neuropathic pain compared to PLWH without neuropathy. We conducted power calculations with the G*POWER software⁹² comparing the area under the curve (AUC) of the change from baseline in pain levels between the three doses of cannabis. The actual analyses will have higher power, since they rely on a longitudinal mixed-effects model. With $n=100$ participants completing the cross-sectional baseline visits, and measured in a within-participant design, as described above, we have 80% power to detect an effect size Cohen's $f=0.180$. This Cohen's f corresponds to a range of group means for the three groups corresponding to a small-to-medium Cohen's $d = 0.382-0.441$. We have 0.61-0.76 power to detect such a pairwise difference as statistically significant in post-hoc analyses (e.g., with Bonferroni correction for post-hoc comparisons). If the completion rate at this stage is 95% (90%) of the initial enrollment of $n=100$, the detectable effect size is Cohen's $f=0.185$ (0.190). These correspond to a range of group means for the three groups corresponding to small-medium Cohen's $d = 0.403-0.465$.

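### Section 7.1 names subject as the only random effect, so Tukey dose contrasts over all time points exceed the stated 5% if same-session readings are positively correlated beyond the subject effect

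*Combined protocol and SAP*

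**What the plan says.** The Schema states that the three doses are "administered once per day on three separate days". Section 4.2 has pain and HRV read 30 minutes before dosing, immediately after it, and at 60, 120 and 180 minutes. The model in Section 7.1 uses the four post-dose times.

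For pain and the endocannabinoid biomarkers, Section 7.1 says "we will use a linear mixed model with subjects treated as a random effect to model the response measures". It describes the method as "incorporating information from observations for each subject at different treatment doses and multiple time points within each dose". The fixed terms are dose, time, dose by time, sequence, time squared and screened covariates. No session or subject-by-dose effect, residual covariance, robust standard error or degrees-of-freedom method is named.

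On the comparisons it says "Differences among doses will be evaluated using the Tukey honestly significant difference (HSD) comparison tests for differences of effects over all time points", and it adds contrasts within each time point. On the level it says "A 5% significance level will be used for all testing".

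Section 7.1 ends: "Within-subject correlation will be accounted for using subject-specific random intercepts and slopes". That sentence directly follows the pain–HRV association model.

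Section 7.1 does not say whether the pain response is the raw NPRS score or the change from the session's pre-dose score. Section 7.4 bases power on "comparing the area under the curve (AUC) of the change from baseline in pain levels between the three doses of cannabis".

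**The concern.** Dose is assigned to a session, not to a reading. The session is therefore the experimental unit for a dose contrast averaged over time, and the error of that contrast must include how much a person's pain shifts from one day to another. A subject intercept absorbs differences between people. It cannot represent the fact that four readings share a day. With no further term, the model treats those four readings as independent given the subject and counts them as four separate pieces of evidence about the dose.

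If people have better and worse pain days, the model's standard errors are then too small. A chance difference between days could be declared a CBD dose effect more often than 5% of the time. The doses are the study's only randomised comparison, and the over-all-time contrast is one of the two kinds of Tukey contrast planned for them.

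**Working it through.** **Inputs from the documents.** n = 100 (Section 7.4); 3 doses, one session each (Schema); 4 modelled readings per session (Section 7.1); Tukey HSD at 5% (Section 7.1).

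**Assumed input.** s, the session share of within-subject variance (session variance divided by session plus reading-error variance). The documents give no value, so a range is shown.

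**Step 1: reproduce the plan's own figures.** A one-way ANOVA power calculation with three groups of n gives 0.7995 at n=100, f=0.180; 0.8007 at n=95, f=0.185; and 0.8001 at n=90, f=0.190. These match the 80% in Section 7.4. That calculation uses one AUC per session, so within-session correlation does not enter it.

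**Step 2: error terms.** Set total within-subject variance to 1, with no true dose effect and balanced data.

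- Between sessions within subject: (100−1)×(3−1) = 198 df, expected mean square (1−s)+4s = 1+3s. This is the correct error for a dose contrast over all time points.
- Within session: 100×3×3 − 3×3 = 891 df, expected mean square 1−s.
- A subject-only model pools the two: [198(1+3s) + 891(1−s)]/1089 = 1 − 297s/1089 = 1 − 3s/11.

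Correct variance divided by model variance is therefore R = (1+3s)/(1−3s/11).

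**Step 3: family-wise error.** The 5% Tukey critical value for 3 means on 1089 df is 3.319. The true error rate is the probability that a studentized range (3 means, 1089 df) exceeds 3.319/√R.

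| s (assumed) | R | √R | Family-wise error |
|---|---|---|---|
| 0 | 1.000 | 1.00 | 5.0% |
| 0.02 | 1.066 | 1.03 | 6.0% |
| 0.05 | 1.166 | 1.08 | 7.6% |
| 0.10 | 1.336 | 1.16 | 10.6% |
| 0.20 | 1.692 | 1.30 | 16.9% |
| 0.30 | 2.069 | 1.44 | 23.3% |

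Example at s = 0.20: R = 1.6/0.9455 = 1.692, and 3.319/1.301 = 2.551. The values at n=90 are the same to within 0.1 point.

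**Step 4: checks by simulation.** Simulating the balanced analysis (20,000 trials per setting) gave 4.9, 7.8, 10.6, 17.2 and 23.2% at s = 0, 0.05, 0.10, 0.20 and 0.30. A session-level error term gave 4.8 to 5.1% throughout. REML fits with continuous time and time squared (2,500 per setting) gave 5.7, 9.9, 17.3 and 22.4% at s = 0, 0.10, 0.20 and 0.30, with simulation error of about 0.4 to 0.9 points.

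**Step 5: if the response is change from the pre-dose score.** The four values in a session then share one subtracted reading. Let v be the pre-dose reading variance relative to a post-dose reading's (assumed). With no other session-level variation the induced share is v/(1+v), so v = 0.25, 0.50 and 1.00 gives 0.20, 0.33 and 0.50. The Step 3 formula gives 16.9, 25.4 and 35.2%. Two separate simulations gave 17.0, 24.9, 35.1% and 16.6, 25.0, 35.6%. A constant day effect cancels in a change score, so these figures are an alternative to the table and do not add to it.

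**Step 6: what is not affected.** Within one time point the correct variance is 1, so the ratio is 1/(1−3s/11): 1.028 at s = 0.10 and 1.089 at s = 0.30. The simulated error at 60 minutes was 5.3% and 6.5%. The dose-by-time test becomes conservative (3.6% at s = 0.10, 1.3% at s = 0.30).

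**The case against.** The strongest reply is that the plan is silent here and does not choose a wrong model. Section 7.1 states the right aim, including several time points within each dose. Nothing in it forbids a session term or a residual covariance, and a careful analyst could add either without breaching the text. That stands as a description: the model is under-specified. It does not remove the point, because the text credits the aim to the subject effect, which cannot deliver it, and nothing requires the missing term.

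A second reply is that the closing sentence on random intercepts and slopes covers the gap. It would do so only if it applied to the dose model and the slopes were subject-specific dose effects. The sentence follows the pain–HRV model and names no slope variable. A subject slope on time would still leave the session effect unmodelled.

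A third reply is that every figure above 5% rests on an assumed variance. That is correct. The table shows sensitivity, and at a 0 to 2% share the effect is negligible.

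Some stronger readings are tempting, and the documents do not support them:

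- A reader might infer that this trial's error rate is in fact 17% or 23%. No session variance is given, so no single figure can be claimed.
- A reader might infer that any correlation inflates the error. Only positive correlation does; at −0.1 the simulated error falls to 1.3%.
- A reader might infer that all the dose tests, or the sample size, are compromised. Steps 1 and 6 show that they are not.

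**Conclusion.** The point holds in conditional form and should be fixed. As written, the Section 7.1 model has no term for session, although dose varies only between sessions. The over-all-time Tukey contrasts therefore miss their stated 5% whenever same-session readings are positively correlated beyond the subject effect. Positive correlation is the expected direction if pain shifts from day to day.

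The missing term and the algebra are certain. The size is not: it ranges from no effect to about 23% over an assumed session share of 0 to 30% on raw scores, or about 16 to 36% if change scores are analysed and the pre-dose variance is an assumed 25 to 100% of a post-dose reading's. The documents do not show which case applies. Naming the term removes the dependence on the unknown variance.

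**What to change.** In Section 7.1, for each Aim 1 outcome read repeatedly within a session, do one of the following:

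1. Add a random effect for session within subject (equivalently subject by dose), or a within-session residual covariance alongside the subject effect, with Satterthwaite or Kenward–Roger degrees of freedom.
2. Analyse one mean or AUC per session.

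The first option keeps every reading in the model, in line with the plan's intention: "All response observations, including information from subjects who do not complete all experimental sessions, will be included in the analyses". The second matches the unit already used for power in Section 7.4.

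As a secondary clarification, state whether the response is raw NPRS or change from the session's pre-dose score.

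The cost is SAP wording and a few lines of code, with no new data and no change in conduct. The statistical price is wider intervals for over-all-time dose effects: from √R, about 8, 16, 30 or 44% wider at an assumed 5, 10, 20 or 30% session share, and essentially unchanged if the share is zero.

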4.2 Cannabis Administration Protocol

Participants will receive vaporized cannabis using Volcano vaporizers (Storz and Bickel) with the aforementioned concentrations of CBD and THC at each of three visits. Allocation assignment of visits will be assigned using randomization schedule prepared by our statistician. The allocation schedule will be kept in the pharmacy and concealed from other study personnel. The cannabis will be stored in a freezer at 20°C until the day before use. At least 12 hours before each session, 800 mg of study cannabis will be thawed. The vaporization session will be performed in a HNRP negative pressure room designed to prevent the vapor from being transferred to rooms in which other occupants of the building are working. Puffs from the vaporizer balloon will be standardized so that a consistent amount is inhaled. This will be done according to a cued-smoking procedure shown to produce reliable increases in plasma THC levels⁶⁵. A nurse will provide instructions to participants to 'inhale' (5 seconds), 'hold smoke in lungs' (10 seconds), and 'exhale' and to wait before repeating the puff cycle (40 seconds). Each participant will inhale 4 puffs at each session, an amount that was well tolerated during our previous human laboratory experiments⁶⁰. We will measure vital signs (heart rate, respiration), pain intensity measured by a 0 to 10 numerical rating scale, and HRV at baseline (30 minutes before cannabis administration), at time zero (immediately after cannabis administration), and at 60, 120, and 180 minutes after drug administration. As a secondary measure of pain relief, we will use the Patient Global Impression of Change (PGIC) that will be measured hourly following administration of study medications. We will also conduct a von Frey assessment. The von Frey tool consists of monofilaments that are applied to the skin until bending of the filament occurs, calibrated to a specific pressure and designed to minimize movement artifacts⁶⁶. Increased pain to von Frey stimulation occurs in NP and clinical trials indicate that cannabis treatment can reduce allodynia on this test⁶⁷. We will include this measure in our battery and assess pain using the VAS as previously reported⁶⁷; the von Frey filament will be applied on the dorsum of the more painful foot until bending is observed for 3 seconds, followed by a VAS pain rating.

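### The Aim 1 dose model has no visit (period) term, so any visit-to-visit trend would misstate the precision of the dose contrasts, in a direction that depends on an allocation balance the plan does not state

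*Combined protocol and SAP*

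**What the plan says.** The schema describes the intervention as "Three doses of cannabis (with varying concentrations of CBD) administered once per day on three separate days". Section 2.0 calls the design a randomised crossover. On visit order, section 4.2 says only: "Allocation assignment of visits will be assigned using randomization schedule prepared by our statistician". Blocking, a Latin square or any other balancing of dose over visits is not mentioned.

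For the analysis, section 7.1 states: "we will use a linear mixed model with subjects treated as a random effect". The fixed terms are dose, time, dose by time, sequence and squared time. Time is minutes within a session: "time (0, 60, 120 and 180 minutes after exposure treated as a continuous variable"). Sequence enters as follows: "Additional terms will also be included for the sequence in which the treatments were administered". The example given in brackets contrasts two doses, not two orders. Of sequence and squared time the plan says: "each of these last 2 terms will be omitted from subsequent models and not reported if nonsignificant". The second model, with time as a categorical factor, has dose and dose by time, "plus a term for sequence if this is significant in the initial model". Visit number is not among the covariates screened at the 0.20 level.

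On incomplete participants: "All response observations, including information from subjects who do not complete all experimental sessions, will be included in the analyses".

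**The concern.** In a three-visit crossover the doses are compared within a person across visits. Anything that changes from visit to visit (familiarity with the procedure, expectation, drift in pain or in response to the drug) is therefore the main nuisance effect, and the usual remedy is a period factor. This model has none.

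Sequence does not fill the gap on either reading. If it means order group, it is constant within a person and cannot remove a visit trend from a within-person contrast. If it means visit order, it could do the job, but the plan removes it, unreported, when it is not significant.

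At stake is the precision of the Aim 1 dose comparisons: lost power in one case, too many false positives in the other. There is little slack, because section 7.4 puts pairwise power at 0.61–0.76.

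**Working it through.** **Inputs.** From the documents: n = 100, three doses, one dose per visit, post-dose times 0, 60, 120 and 180 minutes, a 5% level, and f = 0.180 for 80% power (sections 7.1 and 7.4). Assumed: residual SD 1, a linear trend of b residual SD per visit, and no other visit-level variation until step 4.

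**1. The plan's own figure.** Repeated-measures F test on one value per visit, zero within-person correlation: λ = 100 × 3 × 0.180² = 9.72 on 2 and 198 df gives power 0.797, which reproduces the stated 80%. A three-level visit factor reduces the error df from 198 to 196, and power is still 0.797.

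**2. Dose balanced over visits, one value per visit, visit omitted.** Visit effects of −b, 0 and +b add 2b² per person to the residual sum of squares, or 200b² in all. The residual variance becomes 1 + 200b²/198, while the true variance of the contrast is unchanged. The correct SE for high versus low is √(2/100) = 0.141.

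| b (assumed) | SE factor | Model SE | Overall power at f = 0.180 |
|---|---|---|---|
| 0 | 1.00 | 0.141 | 0.80 |
| 0.25 | 1.03 | 0.146 | 0.77 |
| 0.5 | 1.12 | 0.158 | 0.70 |
| 0.75 | 1.25 | 0.177 | 0.58–0.59 |

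The test is conservative. With four time points per visit the direction is the same: simulated type I error (2,000 runs) was 5.2%, 4.6% and 4.0% at b = 0, 0.25 and 0.5.

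**3. Order by simple randomisation, four time points per visit, subject random effect only.** The position of the high dose minus that of the low dose has mean 0 and variance 2. The contrast therefore has true variance 2/(4 × 100) + 2b²/100. The model spreads the trend over 1,095 residual df (1,200 observations less 100 subjects, 2 dose and 3 time terms), so its SE is √[0.005 × (1 + 800b²/1,095)].

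| b (assumed) | True SD | Model SE | Type I error, normal approximation | Simulated, no visit factor |
|---|---|---|---|---|
| 0.25 | √0.00625 = 0.079 | 0.072 | 7.3% | 7.8% |
| 0.5 | √0.0100 = 0.100 | 0.077 | 13% | 12–16% (two separate simulations) |

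With the visit factor, simulated type I error was 3.8–5.5% across all the cases in steps 2 and 3.

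**4. Random visit-to-visit variation within a person.** Take an assumed visit SD of 0.7 and no trend. The true SD of the contrast is √[2 × (0.49 + 0.25)/100] = 0.122, against a model SE of about 0.082. Simulated type I error was about 18–20%, with or without the visit factor.

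**5. Does dropping sequence matter for the SE?** In one simulated complete, balanced data set (102 participants, b = 0.5), the dose contrast was 0.056 with SE 0.07537, both with and without sequence. Adding visit changed the SE to 0.06918.

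**The case against.** - **No trend is documented.** This is correct. With b = 0 the SEs are right on this point, and at 0.25 SD per visit with balanced order the loss is about 3% in SE. A trend of 0.5 or 0.75 SD per visit means 1.0 or 1.5 SD from the first visit to the third, which is large.
- **Baseline may absorb it.** Section 4.2 takes a baseline 30 minutes before each administration, and the power section works with change from baseline. If the modelled response is change from the same visit's baseline, a shift that is constant within a visit cancels. A trend in response to the drug does not. Section 7.1 does not say which response is modelled.
- **Simple randomisation need not make the SE wrong.** With one value per visit, the true variance is 2(1 + b²)/100 and the model SE tracks it: at b = 0.5, simulation gave 0.158 against 0.160, with type I error 5.4%. Only power is lost. The inflation in step 3 needs several time points per visit combined with a subject-only random effect, but that is the model section 7.1 describes. Its closing mention of random slopes belongs to the model relating pain to HRV.
- **Sequence may mean visit order.** The wording allows this. It narrows the point without removing it, because the term is still tested out and left unreported.

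A reader might infer that the test-based removal of sequence causes the SE problem. It does not (step 5). The objection to that rule is model choice driven by the data, and non-reporting. A reader might also infer material bias because 100 is not divisible by the six orders. Over the six orders, the high-minus-low position differences are +2, +1, +1, −1, −1 and −2. With groups of 16 or 17, the four extra participants add at most 2 + 1 + 1 − 1 = 3, a shift of 3 × 0.5/100 = 0.015 SD at b = 0.5. Imbalance from simple randomisation or from incomplete participants is the more serious route.

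**Conclusion.** The point holds conditionally. Section 7.1 has no visit term in either dose model, and the undefined sequence term does not reliably stand in for one. The documents do not support saying that the dose-contrast SEs are wrong outright. That requires a visit trend in the modelled response, whose size is assumed here.

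Given a trend, the direction depends on the unstated balance of the schedule. Balanced order gives SEs that are too large and a loss of power (steps 1 and 2). Unbalanced order under the model as written gives SEs that are too small and excess type I error (step 3). Because neither the trend nor the balance is known in advance and the protection is nearly free, the term should be prespecified. Random visit variation within a person is a further gap that a visit factor alone does not close (step 4).

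**What to change.** - Include visit (1, 2, 3; categorical) as a fixed effect in every Aim 1 dose model, including the per-time-point model, whatever its p-value.
- Add a visit-within-subject random effect.
- Define sequence, decide in advance whether it is in the model, and report it if it is.
- State how the randomisation schedule balances dose over visits, and whether the response is raw pain or change from the same visit's baseline.

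The visit factor costs 2 degrees of freedom. The rest is SAP wording, with no new data and no change in sample size. The visit-within-subject effect will widen the intervals if such variation exists, and in that case the narrower intervals would have been wrong.
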